**6.5.2.3.2 MLN9708 Treatment Modification**

MLN9708 dose adjustments are allowed based on clinical and laboratory findings. Dose reduction levels of MLN9708 for toxicity are indicated in [Table 6-5](#). Treatment modifications due to MLN9708-related non-hematological toxicities are outlined in [Table 6-9](#).

**Table 6-9. MLN9708 Treatment Modification Due to Non-hematological Toxicities**

Adverse Event (Severity)	Action on MLN9708	Further Considerations
Grade 2 peripheral neuropathy with pain	

• Hold MLN9708 until resolution to Grade <math>\leq</math> 1 or baseline

• MLN9708 may be reinitiated with one dose level reduction.

	
Grade 3 non-hematological toxicity	

• Hold MLN9708 until resolution to Grade <math>\leq</math> 1 or baseline

• MLN9708 may be reinitiated with one dose level reduction

	
Grade 4 non-hematological toxicities	

• Consider permanently discontinuing MLN9708

	With agreement by the sponsor, investigators may consider restarting the therapy for patients continue to benefit from the therapy

#### **6.5.2.3.3 Lenalidomide Treatment Modification**

Lenalidomide dose adjustments are allowed based on clinical and laboratory findings.

Dose reduction levels of lenalidomide for toxicity are indicated in [Table 6-5](#). Treatment modifications due to lenalidomide-related adverse events are outlined in [Table 6-10](#).

**Table 6-10. Lenalidomide Treatment Modification Guidelines Due to Non-hematological Toxicities**

Adverse Event (Severity)	Action on Lenalidomide	Further Considerations
Grade 3/4 toxicities judged to be related to lenalidomide (other than the toxicities listed below)	
 
Hold lenalidomide treatment, and restart at the next lower dose level when toxicity has resolved to <math>\leq</math> Grade 2
 
	Do not dose below 5 mg
Renal dysfunction	
 
Dose reduction, interruption, or discontinuation per lenalidomide package insert
 
	Care should be taken in dose selection/modification in the elderly as they are more likely to have decreased renal function  Monitor renal function regularly
$\geq$ Grade 2 thrombosis/embolism	
 
Hold lenalidomide and start anticoagulation therapy; restart at investigator's discretion after adequate anticoagulation; maintain dose level (No dose modification)
 
	For patients treated with Rd, thromboprophylaxis such as aspirin according to the institutional standard of care is recommended
Angioedema, Stevens-Johnson Syndrome (SJS), and Toxic Epidermal Necrolysis (TEN)		
Grade 2/3 skin rash	
 
Hold or discontinue lenalidomide
 
	
Grade 4 exfoliative or bullous rash or if SJS or TEN suspected	
 
Permanently discontinue lenalidomide
 
	
Any grade angioedema	
 
Permanently discontinue lenalidomide
 
	
Any grade tumor Lysis syndrome	
 
Hold lenalidomide in the same cycle. Upon recovery, lenalidomide can be restarted at the same dose used before interruption.
 
	Monitor closely and take appropriate medical precautions.

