#### **6.4.2 MLN9708 in Combination With Rd**

Treatment of MLN9708 with Rd will be repeated every 28 days as 1 cycle. For a new treatment cycle to begin, the patient must satisfy the following criteria:

- ANC must be  $\geq 1,000 \text{ mm}^3$
- Platelet count must be  $\geq 75,000 \text{ mm}^3$
- All other nonhematological toxicities (except for alopecia) considered related to MLN9708 or Rd must be resolved to  $\leq$  Grade 1 or to the patient's baseline values

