#### **6.4.3 Criteria for Dose Delays**

If a subject fails to meet the criteria for beginning the next cycle of treatment, initiation of the next cycle should be delayed for one week for re-evaluation. If the subject still fails to meet the criteria, the subject should be re-evaluated weekly. The next cycle treatment can be initiated if the subject meets the criteria for initiating the next cycle within 3 weeks of the scheduled initiation of the next cycle. The MLN9708 and lenalidomide starting doses for the next cycle are presented below.

- Reinitiate with one dose level reduction
  - If MLN9708 or lenalidomide treatment was interrupted during the preceding cycle in accordance with “[6.5 Dose Modification](#)” and treatment could not be resumed within the same cycle
- Reinitiate with the same dose level as the preceding cycle
  - If there was no need for dose adjustment in the preceding cycle
  - If MLN9708 or lenalidomide treatment was interrupted during the preceding cycle in accordance with “[6.5 Dose Modification](#)” and treatment could be resumed during the cycle

Should the start of the next cycle need to be delayed for more than 3 weeks because of incomplete recovery from treatment-related toxicity, the patient undergoes the EOS exams, and treatment should be discontinued.

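### A lenalidomide hold for Grade 2 or worse thrombosis/embolism that runs into the next cycle has two different restart doses: unchanged under Table 6-10, one level lower under section 6.4.3

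*Protocol*

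**What the plan says.** Three parts of the protocol bear on the restart dose of lenalidomide in the Rd cohorts.

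- **Table 6-10 (section 6.5.2.3.3), thrombosis/embolism of Grade 2 or worse.** Lenalidomide is held and anticoagulation started. The investigator decides when to restart, once anticoagulation is adequate, and the row fixes the dose: "maintain dose level (No dose modification". It gives no recovery grade and no limit to the current cycle.
- **Table 6-10, tumor lysis syndrome of any grade.** "Hold lenalidomide in the same cycle. Upon recovery, lenalidomide can be restarted at the same dose used before interruption".
- **Section 6.4.3, Criteria for Dose Delays.** This section lists the starting doses of MLN9708 and lenalidomide for the next cycle. The one-level reduction applies "If MLN9708 or lenalidomide treatment was interrupted during the preceding cycle in accordance with" section 6.5 "and treatment could not be resumed within the same cycle". The dose stays the same if treatment was resumed during the cycle, or if no dose adjustment was needed. No type of event is exempted.

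Section 6.5.2.1 applies the level-by-level rules from Cycle 2 and forbids re-escalation after a reduction. Table 6-5 gives the lenalidomide levels as 25, 15, 10 and 5 mg, then discontinuation.

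**The concern.** Table 6-10 is part of section 6.5, so a hold made under it is an interruption of the kind that section 6.4.3 refers to. If a thrombosis hold is still in force when the next cycle starts, both passages apply. One keeps the dose and the other lowers it, and two sites could each follow the protocol and give different doses after the same event.

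Because a reduction cannot be reversed, the difference would last for the rest of that subject's treatment. It would enter the SAP's lenalidomide exposure tables (section 9.4.1: dose intensity, relative dose intensity, and subjects with a prescribed dose reduction). It could also bear on later safety and response data in Cohorts 2 and 4. A reader of those tables could not tell a reduction for intolerance from one that arose from the choice of passage.

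**Working it through.** The plan states no figure on this point, so there is none to reproduce. The check sets the passages side by side and then sizes the dose gap.

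**Step 1. Restart dose when the hold is not resumed in its own cycle**

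| Row of Table 6-10 | Dose under Table 6-10 | Dose under 6.4.3 | Result |
|---|---|---|---|
| Thrombosis/embolism, Grade 2 or worse | Unchanged, no cycle limit | One level lower | Contradiction |
| Tumor lysis syndrome | Unchanged, but the hold is described as within the same cycle | One level lower | Ambiguous |
| Other lenalidomide-related Grade 3/4 | Next lower level | One level lower | Agree |

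The remaining rows defer to the package insert (renal dysfunction), say hold or discontinue without a restart dose (Grade 2/3 rash), or require permanent discontinuation. They raise no conflict here.

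**Step 2. Can a hold cross the boundary?** Section 6.3.2 gives lenalidomide on Days 1 to 21. A hold that begins on Day 15 leaves 21 − 15 + 1 = 7 dosing days in which to resume. Crossing is possible, but the documents give neither the duration of such holds nor how often they cross.

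**Step 3. Planned lenalidomide per full cycle** = daily dose × 21 days.

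| Level at the event | Dose kept | One level lower | Difference |
|---|---|---|---|
| 25 mg | 21 × 25 = 525 mg | 21 × 15 = 315 mg | 210/525 = 40% lower |
| 15 mg | 21 × 15 = 315 mg | 21 × 10 = 210 mg | 105/315 = 33% lower |
| 10 mg | 21 × 10 = 210 mg | 21 × 5 = 105 mg | 105/210 = 50% lower |
| 5 mg | 21 × 5 = 105 mg | Discontinue | No further lenalidomide |

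**Step 4. Effect on relative dose intensity.** SAP section 9.4.1.1 divides the total taken by the total expected at the initial dose. For a subject who was on 25 mg, each later full cycle counts as 525/525 = 100% or 315/525 = 60%.

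The value over the whole treatment moves less. Assume 12 treated cycles, a denominator of 12 × 525 = 6,300 mg, and no other dose change. If *m* later cycles are affected, the two readings differ by 210*m*/6,300:

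- hold in Cycle 2, Cycles 3 to 12 affected (*m* = 10): 2,100/6,300 = 33 percentage points;
- hold in Cycle 11, only Cycle 12 affected (*m* = 1): 210/6,300 = 3.3 percentage points.

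**Step 5. What is not touched.** DLTs are assessed up to Cycle 2 Day 1 (section 6.7.1), and the last pharmacokinetic sample is the Cycle 2 Day 1 predose sample (Table 7-2). The level rules start in Cycle 2, and Cycle 1 problems with Rd go to discussion with the sponsor (section 6.5.2.1). Cohort decisions based on DLTs and the pharmacokinetic data therefore lie outside the conflict.

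**The case against.** The best defence is that the thrombosis row is specific and section 6.4.3 is general. Section 6.4.3 is headed as criteria for dose delays, Table 6-10 is titled as guidelines, and the row expressly rules out dose modification. Reading the row as an exception is natural. However, the protocol states no such precedence, section 6.4.3 exempts no event, and its trigger is failure to resume within the cycle. The investigator's discretion in that row covers when to restart; the dose is stated separately. Nor does the same-dose bullet for cycles without need of adjustment settle it, because the interruption also meets the reduction bullet.

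Three further objections succeed and limit the point.

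- **Tumor lysis.** The row speaks of a hold in the same cycle, and section 6.4.3 also keeps the dose when treatment resumes within the cycle. The two can be read as agreeing, so this row is an ambiguity and not a contradiction.
- **Recovery grade.** A reader might infer a second contradiction, because the general Grade 3/4 row restarts lenalidomide at Grade 2 or less, while section 6.4.2 asks for Grade 1 or less, or baseline. The documents do not support this. Section 6.4.2 is the condition for beginning a new cycle, and the row governs resumption of one drug after a hold. At a cycle boundary, meeting the stricter condition satisfies both. The same holds for thrombosis, where the row permits a restart but does not compel one.
- **Frequency.** A reader might infer that such holds will often cross cycles. No figure supports that. Deep vein thrombosis appears among the drug-related serious events of Study C16005 (section 1.4.2). Here, however, prior or current deep vein thrombosis or pulmonary embolism is excluded in the Rd cohorts, and Table 6-10 recommends thromboprophylaxis. Each Rd cohort plans 3 to 6 subjects, and a later cohort may not be opened.

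**Conclusion.** The contradiction is real for one row, thrombosis/embolism of Grade 2 or worse, with an ambiguity in the tumor lysis row. It arises when a lenalidomide hold from Cycle 2 onward is not resumed in its own cycle. At a first event on 25 mg the two passages differ by 210 mg per full cycle (40%), and the difference persists. In relative dose intensity over 12 cycles this is about 3 to 33 percentage points for the affected subject, under the assumptions of the working.

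It would be too strong to say that Table 6-10 as a whole conflicts with section 6.4.3: its general Grade 3/4 row lowers the dose just as that section does. The exposure tables concerned are descriptive, and few subjects are likely to be affected in cohorts of this size. The conclusion rests on the wording of the passages and not on any assumed event rate.

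**What to change.** Reconcile section 6.4.3 with the thrombosis/embolism and tumor lysis rows of Table 6-10. State which passage governs the lenalidomide restart dose when a hold outlasts its cycle, and put a cross-reference in both places. For tumor lysis, also say whether the same-dose restart is limited to the cycle in which the hold began. The clinical team decides which passage governs; this review takes no position on the dose. The general Grade 3/4 row and section 6.4.2 need no change on this account.

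The cost is a few words in two places. No visit, procedure or analysis is added.

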#### 6.5.2.3.4 Dexamethasone Treatment Modification

Dexamethasone dose adjustments are outlined in [Table 6-5](#). Treatment modifications due to dexamethasone-related adverse events are outlined in [Table 6-11](#).

**Table 6-11. Dexamethasone Treatment Modification Guidelines Due to Non-hematological Toxicities**

Adverse Event (Severity)		Action on Dexamethasone
Gastrointestinal	Dyspepsia, gastric, or duodenal ulcer, gastritis Grade 1-2 (requiring medical management)	If symptoms persist, reduce dexamethasone by 1 dose level as needed.
	> Grade 2	Hold dexamethasone until symptoms adequately controlled. Restart and reduce 1 dose level of current dose.
Cardiovascular	Edema > Grade 2 (limiting function and unresponsive to therapy or anasarca)	Diuretics as needed and reduce dexamethasone by 1 dose level. If edema persists despite these measures, reduce dose another level. Discontinue dexamethasone and do not resume if symptoms persist despite second reduction.
Neurological	Confusion or mood alteration > Grade 2	Hold dexamethasone until symptoms resolve. Restart with 1 dose level reduction. If symptoms persist despite these measures, discontinue dexamethasone and do not resume.
Musculoskeletal	Muscle weakness > Grade 2	Reduce dexamethasone dose by 1 dose level. If weakness persists despite these measures, reduce dose by 1 dose level. Discontinue dexamethasone and do not resume if symptoms persist.
Metabolic	Hyperglycemia > Grade 2	Treatment with insulin or oral hypoglycemics as needed. If uncontrolled despite these measures, decrease dose by 1 dose level until levels are satisfactory.
Acute pancreatitis		Discontinue dexamethasone.

## **6.6 Cohort Transition and Early Stopping Guidelines**

### **6.6.1 Cohort Transition**

Three subjects will be initially enrolled into each dose level in order starting with cohort 1. The sponsor will evaluate the tolerability of MLN9708 dosage in each cohort on the basis of the DLT incidences in consultation with the ESEC, if necessary.

Even if a dosage is considered tolerable and transition to the next cohort is considered feasible, the next cohort may not be studied based on the results of the overseas clinical studies and the current study.

### **1. Cohort Transition From Cohort 1 to Cohort 2**

If no DLT occurs during the DLT assessment period for cohort 1 (the initial dose through before Cycle 2), the dosage will be considered tolerable. If a DLT occurs in one subject during the DLT assessment period, 3 additional subjects will be enrolled into a given dose level to evaluate tolerability in a total of 6 subjects. If DLTs occur in no more than 1 of the 6 subjects, then this dosage will be considered tolerable. If DLTs occur in 2 of 3 subjects, then this dosage will be considered intolerable. If DLTs occur in 2 of 6 subjects, the sponsor will determine the tolerability of this dosage in consultation with the ESEC. Even if a dosage is considered tolerable, the appropriateness of transition to cohort 2 will be determined by the sponsor in consultation with the ESEC as necessary.

### **2. Cohort Transition From Cohort 2 to Cohort 3**

If no DLT occurs during the DLT assessment period for cohort 2, the dosage will be tolerable. If a DLT occurs in one subject during the DLT assessment period, 3 additional subjects will be enrolled into a given dose level to evaluate tolerability in a total of 6 subjects. If DLTs occur in no more than 1 of the 6 subjects, then this dosage will be considered tolerable. If DLTs occur in 2 of 3 subjects, then this dosage will be considered intolerable. If DLTs occur in 2 of 6 subjects, then the sponsor will determine the tolerability of this dosage in consultation with the ESEC. Even if a dosage is considered tolerable, the appropriateness of transition to cohort 3 will be determined by the sponsor in consultation with the ESEC as necessary. If the cohort 2 dosage is found to be intolerable, the sponsor will determine the appropriateness of transition to cohort 3 based on the data obtained from cohort 1 and cohort 2 in consultation with the ESEC.

### **3. Cohort Transition From Cohort 3 to Cohort 4**

If no DLTs occur during the DLT assessment period for cohort 3, the dosage will be tolerable. If a DLT occurs in one subject during the DLT assessment period, 3 additional subjects will be enrolled into a given dosage level to evaluate tolerability in a total of 6 subjects. If DLTs occur in no more than 1 of the 6 subjects, then this dosage will be considered tolerable. If DLTs occur in 2 of 3 subjects, then this dosage will be considered intolerable. If DLTs occur in 2 of 6 subjects, then the sponsor will determine the tolerability of this dosage in consultation with the ESEC. Even if a dosage is considered

tolerable, the appropriateness of transition to cohort 4 will be determined by the sponsor based on the data obtained from cohort 2, in consultation with the ESEC as necessary.

### **6.6.2 Early Stopping Guidelines**

Should the start of the next cycle need to be delayed for more than 3 weeks because of incomplete recovery from treatment-related toxicity (6.4.3 [Criteria for Dose Delays](#)), the patient undergoes the EOS exams, and treatment should be discontinued.

## **6.7 DLT**

### **6.7.1 DLT Assessment Period**

DLTs will be assessed from the first dose until Cycle 2 Day 1 of MLN9708 treatment.

### **6.7.2 DLT-Evaluable Subjects**

DLT-evaluable subjects are defined as follows:

- DLTs  $\geq 1$  during DLT-assessment period.

OR

- Received 3 doses of MLN9708 specified for the applicable cohort and completed the DLT-assessment period.

Subjects whose treatment with MLN9708 was interrupted or reduced in Cycle 1 for reasons other than DLTs are not eligible for DLT assessment in principle.

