### **3.3 Number of Subjects**

Approximately 12 to 24 subjects (3 to 6 subjects in each cohort) will be enrolled in the study.

If any significant protocol deviation that affects DLT assessment is observed or a subject could not complete the protocol-specified MLN9708 treatment during the DLT-assessment period for reasons other than DLTs, the subject will be excluded from the DLT assessment, and additional subject(s) may be enrolled. Moreover, if there seems to be needs for additional data for safety or pharmacokinetics evaluation, the sponsor may decide to enroll additional subjects. See “[10.2 Sample Size Considerations](#) for the sample size justification.

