## **6.3 Dosage, administration method, dosing schedule**

### **6.3.1 MLN9708 administration**

In this study, MLN9708 will be administered orally once weekly for 3 weeks (on Days 1, 8, and 15 and skip Day 22) in a 28-day cycle for up to 12 cycles.

MLN9708 will be taken on an empty stomach at least 1 hour before or no sooner than 2 hours after a meal.

In Cycle 1, MLN9708 will be given according to the dosage and administration specified in this study protocol; no interruption, delays, or reduction will be permitted.

Missed doses of MLN9708 in Cycle 2 and subsequent cycles can be taken as soon as the patient remembers provided that at least 3 days elapses between doses (until Day 4). If a patient vomits after taking MLN9708, the patient should not repeat the dose, but resume dosing at the time of the next schedule.

Once a dose is reduced, no re-escalation will be permitted.

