### **6.7.3 Definitions of DLT**

DLT will be defined as any of the following AEs that are considered possibly related to MLN9708. Toxicity will be assessed according to the CTCAE version 4.03.

1. Grade 4 neutropenia ( $ANC < 500/mm^3$ ) lasting more than 7 consecutive days.
2. Grade 3 or greater neutropenia ( $ANC < 1,000/mm^3$ ) with fever and/or infection, where fever is defined as axillary temperature  $\geq 38.0^\circ C$ .
3. Grade 4 thrombocytopenia (platelets  $< 25,000/mm^3$ ) lasting more than 7 consecutive days.
4. Grade 3 or greater thrombocytopenia ( $< 50,000/mm^3$ ) with clinically significant bleeding, or which requires blood transfusion.

5. A platelet count < 10,000/mm^3.
6. Grade 2 peripheral neuropathy with pain or Grade 3 or greater peripheral neuropathy.
7. Any other Grade 3 or greater nonhematologic toxicities with the following exceptions:
  - Grade 3 or greater arthralgia/myalgia.
  - Grade 3 or greater fatigue lasting less than 7 days.
  - Grade 3 nausea and/or emesis which can be controlled with anti-emetic therapies including anti-emetic prophylaxis. Anti-emetic prophylaxis is defined as an anti-emetic regimen that employs a 5-HT3 antagonist given in standard doses and according to standard schedules. Dexamethasone should not be administered as an anti-emetic.
  - Diarrhea that is controlled with appropriate supportive care
8. A delay of more than 14 days in the initiation of Cycle 2 treatment because of a lack of adequate recovery of MLN9708 related hematological or nonhematologic toxicities.
9. Other Grade 2 or greater MLN9708 related nonhematologic toxicities that, in the opinion of the investigator, require permanent discontinuation of MLN9708.
10. Inability to give at least 80% of the planned lenalidomide doses (Rd combination cohort only) due to the adverse events related to MLN9708.

When a subject experiences any of the above DLTs, MLN9708 therapy should be interrupted within the same cycle after DLT. With agreement by the sponsor, investigators may consider restarting the MLN9708 therapy from next cycle for subjects continue to clinically benefit from the therapy. MLN9708 should be reinitiated in accordance with “[6.4.3 Criteria for Dose Delays](#)”.

The sponsor will consult with the ESEC for the final decision if determination of DLT or subjects’ eligibility for DLT-assessment is difficult.

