7.2 Dose Limiting Toxicity (DLT) Analysis Set

The DLT analysis set will consist of all subjects who experienced at least one DLT during DLT-assessment period (i.e., from the first dose to start of dose in cycle 2), or who received 3 planned doses of MLN9708 and completed the DLT-assessment period. DLT analysis set will be used for DLT analyses.

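### Subjects who miss a Cycle 1 MLN9708 dose through related toxicity short of a listed DLT leave the DLT counts and may be replaced, exactly as if the reason were unrelated

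*Protocol*

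**What the plan says.** **Evaluability.** Protocol 6.7.2 gives two routes into the DLT assessment. One is at least one DLT, whatever number of doses was taken. The other is full dosing: "Received 3 doses of MLN9708 specified for the applicable cohort and completed the DLT-assessment period". It then states that subjects whose MLN9708 was "interrupted or reduced in Cycle 1 for reasons other than DLTs are not eligible for DLT assessment in principle".

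**Exclusion and replacement.** Protocol 3.3 is firmer. Its rule reads: "a subject could not complete the protocol-specified MLN9708 treatment during the DLT-assessment period for reasons other than DLTs, the subject will be excluded". The exclusion applies to the DLT evaluation, and the section lets the sponsor add subjects. Protocol 8.2 has a similar rule for major deviations, and its wording on safety-related reasons can be read either way. SAP 7.2 uses the same two routes, the second being subjects "who received 3 planned doses of MLN9708 and completed the DLT-assessment period", with no qualifier.

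**Cycle 1 dosing.** For MLN9708 in Cycle 1, Protocol 6.3.1 says that "no interruption, delays, or reduction will be permitted".

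**Use of the counts.** Under Protocol 6.6.1, no DLT in 3 subjects, or at most 1 in 6, makes a dosage tolerable. Two in 3 makes it intolerable, and 2 in 6 goes to the sponsor in consultation with the ESEC.

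**The concern.** The dividing line is DLT against everything else. The natural line for a tolerability endpoint is drug-related against unrelated. A subject who skips Day 8 for a family matter and one who skips it because of MLN9708 toxicity are handled alike: both are dropped and both may be replaced.

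For the second subject, the exclusion depends on the outcome that the cohort is meant to measure. With 3 to 6 subjects per cohort, one such exclusion can change the transition decision. The DLT table would not show it, because the subject is absent from both its numerator and its denominator.

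**Working it through.** **Step 1. Does any DLT item catch a missed MLN9708 dose?** From Protocol 6.7.3:

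- Items 1 and 3 need Grade 4 neutropenia or thrombocytopenia lasting more than 7 days. Items 2 and 4 catch cytopenia of Grade 3 or more only with fever or infection (neutrophils), or with clinically significant bleeding or a transfusion (platelets). Item 5 needs platelets below 10,000/mm³.
- Items 6 and 7 cover neuropathy and Grade 3 or greater nonhematologic toxicity. Controlled Grade 3 nausea or vomiting and controlled diarrhea are exempt.
- Item 8 concerns a delay of Cycle 2 by more than 14 days.
- Item 9 needs permanent discontinuation for a nonhematologic toxicity.
- Item 10 is the only item on missed doses, and it concerns another drug: "Inability to give at least 80% of the planned lenalidomide doses (Rd combination cohort only) due to the adverse events related to MLN9708".

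Take platelets of 15,000/mm³ for 5 days, with no bleeding or transfusion and Cycle 2 on time. If the Day 8 dose is withheld, no item is met, three doses were not received, and the subject is excluded. A Grade 2 rash that leads to a temporary hold gives the same result.

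**Step 2. Can this happen although 6.3.1 forbids it?** Protocol 3.3 and 6.7.2 provide for such cases, so the plan expects some. Section 9.2 leaves removal from treatment to the investigator's judgment and lets a subject stop because of an event that he or she finds intolerable. Cycle 1 hematology is scheduled on Days 1, 8, 15 and 22 (7.2.2). A Grade 4 count first found on Day 8 therefore meets a dosing decision before its duration is known.

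**Step 3. The plan's own figure.** 4 cohorts × 3 = 12 and 4 × 6 = 24, which reproduces the 12 to 24 in Protocol 10.2. That section gives no statistical rationale, so there is no stated operating characteristic to reproduce.

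**Step 4. Illustration.** The documents give neither of these two inputs; both are assumptions:

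- d = probability that a subject has a listed DLT
- h = probability that a subject has no listed DLT but misses an MLN9708 dose through related toxicity

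Subjects are taken as independent, and excluded subjects as always replaced. If q is the event probability per counted subject, the chance of a tolerable result without discussion is

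T(q) = P(0 of 3) + P(1 of 3) × P(0 of the next 3) = (1−q)³ + 3q(1−q)⁵.

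A result of 2 in 6 is not counted as tolerable. There are three ways to handle the subjects in question:

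- Excluded and replaced, as written: q = d/(1−h)
- Counted as events: q = d + h
- Counted as evaluable without a DLT: q = d

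With d = 0.20:

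| h | As written | Counted as events | Counted as non-DLT |
|---|---|---|---|
| 0.10 | q = 0.222: 0.470 + 0.190 = 0.660 | q = 0.30: 0.343 + 0.151 = 0.494 | q = 0.20: 0.512 + 0.197 = 0.709 |
| 0.20 | q = 0.25: 0.422 + 0.178 = 0.600 | q = 0.40: 0.216 + 0.093 = 0.309 | q = 0.20: 0.709 |

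The chance that at least one of the first three subjects is excluded in this way is 1 − (1−h)³, which is 0.271 for h = 0.10 and 0.488 for h = 0.20.

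**The case against.** The case on the other side has several parts.

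- **The Cycle 1 ban makes such a hold a deviation, so it should be rare.** This bears on frequency, and h is indeed unsupported by the documents. It does not remove the gap, because 3.3 and 6.7.2 settle these cases by exclusion. The interruption limits in 6.5.1.1.1 (platelets below 30,000/mm³, ANC below 750/mm³) apply only from Cycle 2, so they say nothing about how often Cycle 1 doses are missed.
- **The rule is softened.** Section 6.7.2 states it as a principle, and 6.7.3 sends difficult eligibility questions to the ESEC. That stands for 6.7.2, but 3.3 and SAP 7.2 carry no such softening, and consultation is not required where the text already gives an answer.
- **The decision is not mechanical.** Protocol 3.1 lets the sponsor weigh safety data including DLT incidence, and 6.6.1 leaves transition to the sponsor even after a tolerable count. This is a genuine safeguard. However, the numerical rule in 6.6.1 runs on DLT counts, and these subjects are not in them.
- **Exclusion can be the stricter choice.** This is correct. Against counting these subjects as non-DLT, the written rule lowers the chance of a tolerable result (0.660 or 0.600 against 0.709).

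A reader might also infer more than the documents support:

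- *That cohorts are judged only on subjects who tolerated all three doses.* They are not: a subject with a DLT is evaluable after any number of doses.
- *That these subjects leave the primary endpoint.* Only the DLT component loses them. They stay in the safety analysis set for adverse events, laboratory tests and the other primary safety measures.
- *That Study C16004 gives h, since 6 of 32 subjects (19%) discontinued for possibly related events.* That figure covers all cycles and doses up to 3.95 mg/m², above the MTD of 2.97 mg/m². Some of those cases would be listed DLTs here under item 9.
- *That item 10 contradicts the exclusion rule.* The contrast is notable, but 6.5.2.1 only discourages Rd changes while barring MLN9708 changes in Cycle 1, so a missed-dose item for lenalidomide alone can be defended.

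**Conclusion.** The gap is in the text. Three sections exclude, and one of them expressly allows replacement of, subjects whose Cycle 1 MLN9708 was not completed for any reason short of a listed DLT. No DLT item covers an MLN9708 dose missed through related toxicity below that line. The exclusion from the counts in 6.6.1 is therefore partly outcome-dependent.

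The direction is conditional. If the missed dose reflects intolerance, the rule is lenient: at d = 0.20 by 0.660 − 0.494 = 0.166 for h = 0.10, and by 0.600 − 0.309 = 0.291 for h = 0.20. If it does not, the rule is slightly strict. These figures rest on assumed d and h, independent subjects and certain replacement, so they show sensitivity and do not estimate the bias. A statement that cohorts will be passed too often, without that condition, would go beyond the documents.

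**What to change.** 1. In Protocol 3.3, 6.7.2 and 8.2 and in SAP 7.2, limit automatic exclusion and replacement to reasons unrelated to MLN9708 toxicity.
2. Require an ESEC ruling, DLT or not DLT, on every subject with a Cycle 1 MLN9708 dose missed, held or reduced for an MLN9708-related event. The ruling comes before the subject is excluded or replaced and before the cohort is called tolerable. Protocol 3.5.1 has the ESEC act at the sponsor's request, so the requirement has to be written down.
3. Do not count a subject who is ruled not DLT, but did not receive three doses, as a full non-DLT subject. Otherwise under-dosed subjects would dilute the denominator and move the rule toward the 0.709 column.
4. Add one row to the DLT table in SAP 9.4.2.2, with all such subjects in the denominator and counted as events.
5. Reconcile Protocol 3.3, 6.3.1, 6.7.2, 6.7.3 and 8.2 with SAP 7.2. Sections 3.3 and 6.7.2 provide for Cycle 1 interruptions that 6.3.1 does not permit, and 6.7.3 itself calls for interruption after a DLT.

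How such events are classified clinically is for the sponsor and the ESEC, and none of these changes sets a dosing rule. With steps 2 and 3, the chance of a tolerable result lies between the as-written and counted-as-events columns, depending on how many cases are ruled DLTs. The cost is wording in four sections plus the reconciliation, one table row, some extra ESEC work, a DLT rate that may look less favourable, and more frequent expansion from 3 to 6 subjects.
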